Level of Function 1	Bed Activity
Level of Function 2	Able to Sit
Level of Function 3	Able to Stand
Level of Function 4	Walks < 20 feet
Level of Function 5	Walks > 50 feet

The current mobility practices and LOF assessment for patients admitted to the CICU of the Jewish General Hospital were reviewed by a nurse educator on two separate dates as part of continuous quality improvement requested by the quality of care committee of the division of cardiology. We looked at a convenience sample of patients in the CICU on two separate dates. There were 26 patients in the analysis (mean age 71.7 years old, standard deviation (SD) ± 10.9 , female 38.4% (n=10)). There were 10 patients (38.5%) who would not be initially eligible for entry into the study (see eligibility criteria below; four due to age, two on noninvasive or invasive ventilation, two with a transvenous pacemakers, and two who were not hemodynamically stable). For patients who were initially eligible for the study, the mean prehospital LOF was 4.7 (SD ± 0.6) and the mean LOF on CICU admission was 2.3 (SD ± 1.2). Of the eligible patients, 14 patients (87.5%) said they would agree to participate in an EM study and 12 patients (75%) were followed prior to hospitalization by a hospital-affiliated cardiologist.

VI. METHODS

Design, participants and setting

An EM program is being developed as a quality improvement project in conjunction with the Quality and Safety Committee of the Division of Cardiology at the Jewish General Hospital (JGH). For our study, we will perform a prospective, pre/post-EM intervention study in adults aged ≥ 60 years old admitted to the CICU at the JGH. During a 3-month period, we will prospectively enrol patients to the pre-intervention cohort. The EM intervention will then be implemented. During a 12-month period, we will prospectively enrol patients to the intervention cohort. 1 and 12 months following hospital discharge, patients in the pre-intervention and post-intervention cohorts will be contacted by phone by a member of the research team to assess for functional status and quality of life measures.

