housed in the Frailty Assessment Unit of the JGH's cardiovascular ward and can be used at the point of care. The BIA scales provide a full analysis of body composition in less than 1 minute, including determination of skeletal muscle mass. There are no risks associated with the bioimpedance scale, except for patients with a permanent pacemaker or defibrillator, who will be excluded from this trial (the reason being that bioimpedance scale currents may disrupt the functioning of pacemakers or defibrillators).

Post-discharge follow-up

One month and 12-months post-discharge a member of the research team will call participants by phone to assess for health-related quality of life and functional status. The member of the research team will determine the current LOF and administer the Short-Form 36-Item Health Survey (SF-36) and Barthel index.

Outcome Measures

The primary outcome will be the LOF at CICU discharge and at 1 and 12 months post-hospitalization. Secondary outcomes are (1) Short Form (SF)-36 physical component summary score at 1 and 12 months, (2) SF-36 mental component summary score at 1 and 12 months, (3) Barthel index score at 1 and 12 months, (4) length of hospital stay, and (5) discharge to healthcare facility (including rehabilitation facility, convalescence, transfer to another acute care facility, and long-term care placement).

The SF-36 is a patient-reported survey of health and is the most widely used health-related quality of life instrument.⁵³ The physical and mental component scores are subsets of the SF-36 with score ranges from 0-100 and are calibrated for an average score of 50, using Canadian normative data, with higher scores indicating less disability.⁵⁴ The Barthel index is a disability measure validated in elderly cardiac patients that incorporates ten activities of daily living (i.e., feeding, dressing, incontinence).^{55, 56} Only two components of the Barthel index address mobility issues (transfer and mobility), so there is minimal direct overlap with the LOF scale score. The score range is 0–20, with lower scores indicating increased disability.

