From the pilot data, we conservatively estimate that about one-third of patients will not be eligible for the study and about 70% will agree to participate. We estimate that the loss of patients to 12 month follow-up will be approximately 10% as the vast majority of CICU patients are followed by hospital-affiliated cardiologists prior to admission or are assigned to one following CICU discharge. Given these estimates, approximately 75 patients are expected to be enrolled and followed during the pre-intervention period and 300 patients are expected to be enrolled and followed during the 12 month intervention period.

Data Analysis

Since the response variable, LOF mobility, is an ordinal variable measured at different timepoints, a cumulative logit model for repeated measurements will be fitted using generalized estimating equations. The model permits us to take into consideration the structure of the correlation between the observations. The model will then be adjusted using covariates of interest, such as age, sex, EM adherence, time spent lying in bed, and illness severity score. Predictors of change in LOF during CICU stay and following hospitalization will be assessed using linear regression. Predictors of EM adherence will also be evaluated using linear regression. All statistical analyses will be performed using SAS version 9.4 by [name], a senior biostatistician affiliated with the Lady Davis Institute Center for Epidemiology.

VII. RESOURCE AVAILABILITY AND SUPPORT

The CICU at the JGH has 16 beds equipped for advanced hemodynamic support and 32 ward beds with telemetry available. Patients are admitted to the CICU mainly for acute primary cardiovascular disease.

The nurse champion's role is to attend EM team meetings, provide education to nursing and clinical partners, and ensure nursing adherence to the protocol. A review of the CICU environment conducted with physiotherapists from the EM team has ensured that the CICU is already equipped with the standard equipment necessary for patient mobilization, particularly for bedbound and immobile patients, and nurses have been trained to use the equipment.

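### The GEE for LOF at 1 and 12 months has no stated weighting or imputation for patients not reached by phone; bias is small at the planned 10% loss and material only if loss differs between cohorts

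*Combined protocol and SAP*

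**What the plan says.** Section VI, Outcome Measures: "The primary outcome will be the LOF at CICU discharge and at 1 and 12 months post-hospitalization". Under Post-discharge follow-up, a team member "will call participants by phone to assess for health-related quality of life and functional status", and on that call "The member of the research team will determine the current LOF and administer the Short-Form 36-Item Health Survey (SF-36) and Barthel index". The Design paragraph applies the same route to both groups: "patients in the pre-intervention and post-intervention cohorts will be contacted by phone by a member of the research team". No other source for post-discharge LOF is described.

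Under Data Analysis, "a cumulative logit model for repeated measurements will be fitted using generalized estimating equations", with the justification that "The model permits us to take into consideration the structure of the correlation between the observations". The adjustment covariates are given as examples: age, sex, illness severity, adherence to the programme and lying time. Earlier LOF and CFS are not among them, although Data Collection Procedures lists both as captured.

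The only statement on loss is in Availability of Participants: "We estimate that the loss of patients to 12 month follow-up will be approximately 10" (per cent). It is supported by cardiologist follow-up and is not split by cohort, or between deaths and missed calls. The document states no missing-data assumption, weighting, imputation or sensitivity analysis.

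**The concern.** An unweighted GEE uses the LOF values that happen to be observed. It is consistent only if, given the covariates in the model, whether a patient is reached does not depend on LOF, either the values already recorded or the current value that would have been heard on the call.

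There is reason to doubt that condition. The Background links frailty to long-term disability, institutionalization and readmission, and surviving patients in those states may be harder to interview. If they drop out of the later time points, each cohort looks better than it is. The between-cohort odds ratio then shifts whenever the dropping-out is not balanced. More selective loss in the pre-intervention cohort pulls the apparent effect down, and more selective loss in the intervention cohort pushes it up.

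The point concerns living patients who are not reached. How death enters the LOF analysis is a separate question.

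**Working it through.** **1. Numbers at stake.** The plan projects 75 and 300 patients enrolled and followed. Its inputs do not reproduce these counts: 1,034 × 2/3 × 0.7 × 0.9 = 434 a year, or 109 per quarter. Removing the one in five stays under 24 hours gives 347 and 87. The stated counts are approximate and lower than their inputs imply, the 4:1 ratio matches 12:3 months, and nothing below depends on the gap. If 75 and 300 are counts after 10% loss, enrolment is 75/0.9 = 83.3 (84) and 300/0.9 = 333.3 (334), so about 9 and 34 patients are lost.

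**2. Bound without assumptions.** With 10% lost in each cohort, the true share above any LOF cut-point is 0.9 × observed share + 0.1 × u, where u (between 0 and 1) is the share among the lost. The true between-cohort difference therefore lies within 0.9 × observed difference ± 10 percentage points. This is a worst case, not an expectation.

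**3. Yardstick.** For a proportional-odds comparison, the information is n₁n₂n / [3(n+1)²] × (1 − Σp³). With 75, 300 and n = 375, the first factor is 8,437,500 / 424,128 = 19.89. The LOF distribution is not in the document, so two extremes are assumed:
- uniform over six levels: Σp³ = 6/216 = 0.028, information 19.34, standard error 0.23;
- 75% in the top level and 5% in each other: Σp³ = 0.4225, information 11.49, standard error 0.30.

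**4. Large-sample simulation.** There were 400,000 patients per cohort and six LOF levels. Assumptions not in the document: the LOF distributions, latent correlation 0.6 between discharge and 12 months, discharge odds ratio 2.0, true 12-month odds ratio 1.50, and odds of loss multiplied by 2.0 or 3.3 for each one-level lower discharge LOF. The 12-month odds ratio was estimated from reached patients only, as an unweighted independence GEE with a separate cohort effect at each time would do.

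| Loss mechanism | 10% loss* | 20% loss* | 30% loss* |
|---|---|---|---|
| Unrelated to LOF | 1.49 | 1.51 | 1.51 |
| Same dependence in both cohorts | 1.45–1.48 | 1.40–1.45 | 1.38–1.43 |
| Pre-intervention cohort only (multiplier 3.3) | 1.29 | 1.14 | 1.01 |
| Intervention cohort only (multiplier 3.3) | 1.78 | 2.03 | 2.26 |

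*Control-cohort loss in the same-dependence row; loss in each cohort in the other rows.

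Other assumed LOF distributions, at 10% with loss tracking LOF in one cohort, give about 1.26–1.35 (pre-intervention) or 1.70–1.85 (intervention). A weaker dependence, multiplier 1.5, reaches only about 1.42 or 1.60. With the same dependence in both cohorts and no cohort difference at discharge or 12 months, there is no bias.

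**5. Size against the standard error.**
- Shared mechanism at 10%: ln(1.50/1.45) = 0.034 and ln(1.50/1.48) = 0.013, so 0.013/0.30 to 0.034/0.23, about 0.04 to 0.15 standard errors.
- One cohort only at 10%: from ln(1.50/1.35) = 0.105 to ln(1.85/1.50) = 0.210, so 0.105/0.30 to 0.210/0.23, about 0.35 to 0.91 standard errors.

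**6. Does the remedy work?** Weighting by cohort and discharge LOF returned 1.49–1.51 in every scenario where loss depended on discharge LOF. If loss also depends on the unseen 12-month LOF, the unweighted result is 1.43 at 10% and 1.39 at 20%. Weighting recovers only part of this (1.47 and 1.44).

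**The case against.** The strongest defence is that the problem is negligible at the plan's own figure. With 10% loss and a common mechanism, the shift is at most about 0.15 of a standard error. That stands, and it limits the weight of the point.

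Second, the document gives no evidence that the cohorts will be lost differently. Both are called in the same way by the same research-assistant role, the follow-up periods overlap in the timetable, and the assistant's funding is renewable for up to three years. A reader might infer that the 12-month effect could be halved. That needs about 19% to 26% loss in the pre-intervention cohort against 8% to 10% in the other, where simulation shows the log odds ratio falling by 11% to 56%. Nothing in the document points to such a doubling, so those figures are an assumed extreme. What remains is that equal loss is not assured: the cohorts reach 12 months in different calendar periods, and one assistant at 20 hours a week also handles consent, data extraction, audit and reporting.

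Third, a phone call does not require mobility, patients with prehospital LOF 0 to 2 are excluded, and participants are expected to be competent at consent. This weakens the link between low LOF and not being reached, but does not exclude later decline. The 10% may also include deaths, in which case fewer survivors are missed than assumed here.

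Fourth, a reader might infer that the plan forbids information from anyone but the patient. It does not: patients are the named contact, and the text is silent on caregivers. The covariate list is also open-ended, so earlier LOF could be added, but as written it is not named.

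**Conclusion.** The point holds in a limited form. The planned GEE for 1- and 12-month LOF relies on being reached having no relation to earlier or current LOF, given the model covariates. The plan neither states that condition nor uses the LOF and CFS data that would relax it. At about 10% loss with a shared mechanism the bias is small (1.50 becomes about 1.45 to 1.48). It becomes material if the mechanism or the rate of loss differs between cohorts: about 1.26 to 1.35 or 1.70 to 1.85 at 10% loss tracking discharge LOF in one cohort only. These sizes rest on assumed LOF distributions, correlation, effects and strength of dependence.

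A reader might conclude that the later primary comparisons will be biased. The document supports only that they can be, because a difference in loss between cohorts is possible but undocumented. This is a desirable improvement, not a defect that undermines the study.

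**What to change.** 1. For the 1- and 12-month comparisons, pre-specify GEE weighted by the inverse probability of being reached, or GEE after multiple imputation. Keep that model small, given about 75 pre-intervention patients: cohort, most recent observed LOF (CICU discharge or 1 month) and CFS. Apply it to survivors, check vital status of unreached patients in the records available, and handle deaths under a separate rule, so that LOF is not imputed for patients who have died. A random-effects cumulative logit model is not an equivalent substitute, because its odds ratio is patient-specific whereas that of GEE is population-averaged.
2. Where consent and ethics approval allow, accept LOF and Barthel, but not SF-36, from a caregiver when the patient cannot be interviewed. Flag the source and repeat the analysis without proxy reports. Settle this before calls begin, since a missed 1-month observation cannot be recovered.
3. Report loss by cohort and by CICU-discharge LOF, so that readers can judge whether it was balanced.

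Cost: slightly wider intervals, a little more analysis work, possible consent or ethics wording, and possible differences between proxy and self-report. No extra patients or visits are needed. If loss depends on the unseen current LOF, weighting or imputation removes only part of the bias.

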Prior to the implementation of the EM intervention, nurses will ascertain and record the prehospital LOF, admission LOF, and LOF on the day of CICU transfer (Appendix A), but will continue usual mobilization practices. Patients who meet eligibility criteria for the EM intervention will be prospectively enrolled over a 3-month period (“pre-intervention cohort”) by a member of the research team during CICU admission. Informed consent will be obtained by a member of the research team. Following discharge, a member of the research team will review the medical record to extract demographic data (age, sex), comorbid illnesses, primary admission diagnosis, frailty status, adverse events during mobilization (falls, dislodgements, and injuries), mobilization activities, length of critical care unit stay, length of hospital stay, mortality, and discharge location.

Intervention

On admission to the CICU, the patient’s treating nurse will assess the patient for the EM program. Patients participating in the EM program will be assessed for enrolment in our study by a member of the research team and will obtain informed consent during CICU admission (“intervention cohort”). The potential participants are likely to be competent and medically fit to be approached for informed consent as patients who are not medically fit will be excluded from the early mobilization program based on clinical factors, which include hemodynamic criteria.

The EM program consists of a progression of functional activities from LOF 0 (lowest mobility) to 5 (highest mobility). Each LOF has 3 primary activities designed to promote the patient to the next level. The nurse will begin with mobility activities based on the LOF that matches the patient’s current status. The nurse and clinical partner will attempt and/or complete each LOF activity once per shift. Physiotherapy assistance is available if required, although not obligatory. Nurses will also provide documentation and education to patients and families on

how to perform and assist with certain activities. LOF, activity attempts/completion, and adverse safety events will be recorded on an EM flowsheet. The intervention will start while the patient is in the CICU and will continue until discharge from the CICU.

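### The primary level-of-function model does not name admission level of function as a covariate, so a real starting difference between the two sequential cohorts would pass into the apparent EM effect, and power is lost

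*Combined protocol and SAP*

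**What the plan says.** The two cohorts are enrolled one after the other. Under Design, participants and setting, "we will perform a prospective, pre/post-EM intervention study in adults aged" 60 or over: three months of enrolment before EM starts and 12 months after. Nothing is randomised.

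Outcome Measures states: "The primary outcome will be the LOF at CICU discharge and at 1 and 12 months post-hospitalization". For the analysis, "a cumulative logit model for repeated measurements will be fitted using generalized estimating equations" (Data Analysis). The same paragraph continues: "The model will then be adjusted using covariates of interest, such as age, sex, EM adherence, time spent lying in bed", and the sentence closes with illness severity. The list is given as examples. It contains neither admission nor prehospital LOF.

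On whether a starting LOF will exist:

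- **Pre-intervention cohort:** stated outright. Under Pre-intervention, "nurses will ascertain and record the prehospital LOF, admission LOF, and LOF on the day of CICU transfer".
- **Intervention cohort:** no equivalent sentence, but four statements imply it. Prehospital LOF is needed to apply the study exclusions (Design, participants and setting). The nurse starts with activities matched to the patient's present LOF, and LOF goes on the EM flowsheet (Intervention). LOF assessments are extracted from the record for every subject (Data Collection Procedures). A regression on change in LOF during the CICU stay is planned (Data Analysis), and it needs a starting value.

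In the site's own pilot review (V. Preliminary Studies), among patients who would have been eligible, "the mean LOF on CICU admission was 2.3" with an SD of 1.2. Prehospital LOF had mean 4.7 and SD 0.6.

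**The concern.** A patient's LOF on admission is likely to be among the strongest predictors of LOF at CICU discharge. In a non-randomised before-and-after comparison it is the first variable one would want balanced or adjusted for. If the intervention cohort happened to arrive more mobile, an unadjusted model would credit EM with the difference. If it arrived less mobile, a real benefit would be hidden.

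A difference is plausible. One cohort covers a single quarter and the other a full year. Entry is also described differently: patients who meet the EM eligibility criteria in the first cohort, and patients taking part in the EM program in the second.

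Even with perfectly balanced cohorts, leaving out a strong predictor costs power, and the smaller cohort has only about 75 patients.

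Aim 4 has the same gap. A patient with a low starting LOF will probably spend more time lying in bed and also leave the CICU at a lower LOF. Without admission LOF in the model, the association of lying time with function partly restates where the patient began.

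**Working it through.** **The plan's own figures.** The plan gives no alpha, power or target effect. Its only size figures are the expected 75 and 300 patients (Availability of Participants). The stated rates give 1,034 × 0.8 × 2/3 × 0.7 × 0.9 = 347 a year, or 87 in three months. Using the pilot's 61.5% eligible instead of 2/3 gives 320 and 80. The forecast is described as approximate and conservative, and no rate is given for the cardiac surgery exclusion, so I do not call this an error. I use 75 and 300 as stated.

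**Inputs.**

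- From the documents: n = 75 and 300; admission LOF mean 2.3, SD 1.2; scale 0 to 5.
- Assumed: outcome SD 1.2; admission-outcome correlation ρ = 0.3, 0.5 or 0.7; two-sided alpha 0.05; effect 0.4 levels; admission difference 0.3 levels; mean outcome LOF 3.5 in the simulation.

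**Scale of imbalance.** SE of the admission difference = 1.2 × √(1/75 + 1/300) = 0.155, so the 95% chance range is ±1.96 × 0.155 = ±0.30 levels. A 0.3-level difference is therefore at the edge of what chance would produce. It is used below as a fixed, true difference.

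**Bias, linear approximation.** Spurious effect = ρ × 0.3 = 0.09, 0.15 and 0.21 levels. Dividing by 0.155 and taking both tails at 1.96 gives rejection rates of 8.9%, 16.2% and 27.3% with no EM effect.

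**The planned model type.** A cumulative logit model at one timepoint was simulated, 300 runs per scenario. LOF was rounded and limited to 0 to 5. The model contained cohort alone, or cohort plus admission LOF as a linear term.

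| ρ | Rejection, true 0.3 admission difference, no EM effect: unadjusted | Adjusted | Power, 0.4-level effect, balanced cohorts: unadjusted | Adjusted |
|---|---|---|---|---|
| 0.3 | 7.7% | 5.3% | 66.3% | 69.7% |
| 0.5 | 14.7% | 5.7% | 67.0% | 80.0% |
| 0.7 | 28.3% | 6.0% | 69.3% | 89.7% |

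The simulation error near 5% is √(0.05 × 0.95 / 300) = 1.3 percentage points, so the adjusted rates are compatible with 5%. At ρ = 0.3 the inflation is small. It agrees in direction and rough size with the linear figure of 8.9%.

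**Where the power comes from.** In the balanced runs the mean log odds ratio (SE) was:

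| ρ | Unadjusted | Adjusted |
|---|---|---|
| 0.3 | 0.562 (0.234) | 0.587 (0.236) |
| 0.5 | 0.569 (0.234) | 0.650 (0.240) |
| 0.7 | 0.580 (0.234) | 0.791 (0.248) |

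The SE does not fall; it rises slightly. Power improves because omitting a strong predictor pulls the log odds ratio toward zero.

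**The case against.** The strongest reply is that the covariate list is open. Admission LOF is not excluded, and a biostatistician might well add it. Illness severity and age are listed and may absorb part of a starting difference. The plan also models change in LOF during the CICU stay, which uses the starting value.

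Part of this stands. The defect is incomplete pre-specification, not a decision against adjustment, and the simulated bias is upper-end because it contains no other covariates. But an open list lets the choice be made after the results are seen. The change regression looks for predictors and does not replace the primary cohort comparison. Illness severity is at best a partial stand-in for mobility.

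Two further cautions also stand. Recording of admission LOF in the intervention cohort is inferred, though strongly. The SD of 1.2 rests on 26 − 10 = 16 eligible patients in a two-date convenience sample; under normality its 95% interval is about 0.89 to 1.86.

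A reader might infer more than the documents support:

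- **That chance imbalance alone inflates the type I error.** It does not, because it is already in the unadjusted SE. With no systematic difference, a simulated unadjusted comparison in a linear approximation rejected in 4.5% to 5.1% of trials. The 8% to 28% applies only if a true difference of that size exists, and the documents give no figure for drift.
- **That adjustment shrinks the SE.** This holds in a linear model, not in the planned cumulative logit model, as the working shows.
- **That the pre-EM values might enter as responses and dilute the effect.** Data Analysis says only that LOF "is an ordinal variable measured at different timepoints". Outcome Measures names three timepoints, all after EM can begin, and no common cohort effect or weighting is stated.
- **That prehospital LOF is equally needed.** The exclusions restrict it to levels 3 to 5 and the pilot mean is near the ceiling, so it adds little.

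**Conclusion.** The point holds as a gap in pre-specification with a real consequence. The primary comparison is between non-randomised sequential cohorts, and the outcome's own baseline is not named in the model. The cost in false positives depends on a true starting difference, which the documents neither report nor rule out. It ranges from slight at a correlation of 0.3 to serious at 0.7. The cost in power does not depend on any imbalance: about 3 to 20 percentage points across the same range (69.7 − 66.3 to 89.7 − 69.3).

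Correlation, outcome SD, alpha and effect size are all assumptions. The simulation covers one timepoint, not the full repeated-measures model, so the figures show direction and rough size only. Adjustment deals with starting mobility. It does not deal with other changes in case mix or care between the two periods, which remain a limitation of the design.

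**What to change.** Add to Data Analysis: the responses in the primary LOF model are LOF at CICU discharge, 1 month and 12 months, in line with Outcome Measures; admission LOF enters that model, and the model that answers the Aim 4 lying-time question, as a pre-specified covariate. State in advance whether it enters as linear or categorical. Prehospital LOF may be added but is optional. Under Intervention, add a sentence confirming that admission LOF is recorded as in the pre-intervention cohort.

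In the report, note that the adjusted odds ratio is conditional on admission LOF, and that adjustment does not remove other secular differences between the cohorts.

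The cost is a few sentences. No new measurement appears to be needed, provided the intervention flowsheet captures LOF on admission, as the plan implies.
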